1. STUDY OBJECTIVES

1.1 Study Purpose

The purpose of this study is to evaluate the changes in clinical and imaging outcomes following arthroscopic treatment of chondral lesion(s) by Radiofrequency-Based debridement or Mechanical Debridement in subjects 18-50 years of age.

1.2 Primary Objective

The primary objective is to evaluate the efficacy of Radiofrequency-Based debridement vs. Mechanical Debridement for the treatment of articular cartilage lesions.

1.3 Secondary Objective

The secondary objectives are to evaluate imaging and additional subjective and objective clinical outcomes.

2. STUDY ENDPOINTS

2.1 Primary Endpoint

The primary endpoint is to evaluate the change in Knee and Osteoarthritis Outcome Scores (KOOS) activity subscale at Week 52 post-operative compared to baseline

2.2 Secondary Endpoints

- Change in Visual Analogue Scale (VAS) scores from baseline
- Change in International Knee Documentation Committee (IKDC) Subjective Knee Evaluation Form scores from baseline
- Change in International Knee Documentation Committee (IKDC) Objective Knee Examination Form scores from baseline
- Change in Marx Activity Rating Scale from baseline
- Change in Work Productivity and Activity Impairment Questionnaire for Articular Cartilage Knee Injuries V2.0 (WPAI V2.0) from 1 week post-op to 6 weeks post-op
- Subject Satisfaction at Week 52 post-op

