4. PROCEDURES

4.1 Research Design

This is a non-inferiority, prospective, single blinded, randomized, single-center study design with enrollment of 82 randomized subjects (to assure 70 subjects complete the study). The sample size of 82 participants was calculated from a power analysis. The study was powered to detect at least a seven point change in KOOS pain score based on achieving 80% statistical power to detect a non-inferiority margin. Study duration will be until the last subject enrolled reaches 52 weeks post-operative.

The 82 randomized subjects will be randomized at a 1:1 ratio into the Werewolf Coblation wand treatment group or mechanical debridement treatment group. Subjects will be blinded to their treatment assignment until they complete all study visits. Upon withdraw from the study, termination from the study, or new or recurrent symptoms requiring a subsequent arthroscopy, the blinded assignment will be revealed to the subject.

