4.2 Subject Recruitment and Screening

Subjects will be voluntarily recruited from the Principal Investigator or Sub-Investigator population and/or referring physicians.

Subjects will be screened to determine if they meet all inclusion and no exclusion criteria. If all entry criteria are accomplished, the subject will be eligible to participate in the study.

Eligible subjects will be provided an IRB approved Informed Consent Form for review and signature. Each subject will have a physical assessment by the surgeon and will complete all patient reported outcomes (KOOS, VAS, IKDC subjective, Marx). X-rays and MRI will be attained if previous imaging is greater than 3 months old.

All potential subjects screened for eligibility will be listed on the electronic Screening and Enrollment Log. The electronic Screening and Enrollment Log will document the date of screening, the results of screening, and the primary reason for excluding the subject. The electronic Screening and Enrollment Log will be kept on the research shared drive (encrypted and located behind the OSUMC firewall). The log will be password protected.

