4.4 Measurement/Instrumentation

The change in the KOOS activity subscale will be the primary study endpoint. Secondary outcomes include time to return to work/activity and time to return to no pain. Baseline MRI will be compared to MRI at 52 weeks to evaluate knee morphology, cartilage signal, osteophytes, bone marrow edema, subarticular cysts, effusions and loose bodies. The international cartilage repair score will be used.

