4.5 Detailed Study Visits

Screening

- Confirm written informed consent prior to screening procedures
- Inclusion/exclusion criteria
- Physical assessment by surgeon – IKDC objective
- Demographics
- Medical and surgical history

- X-rays unless provided (must be less than 3 months old)
- MRI unless provided (must be less than 3 months old)
- Patient reported outcomes
 - KOOS, VAS, IKDC subjective, Marx

Date of surgery

- Arthroscopic inclusion/exclusion criteria
 - No articular cartilage lesion present that requires treatment
 - Evidence of previous chondral treatment not noted at screening
 - Chondrocalcinosi
- Randomization
- Surgery performed

10 days (7 days-14 days post op)

- Explanation of the weekly online data to be collected on RedCap
 - KOOS activity, VAS, return to work/activity (WPAI V2.0). [To be completed weekly from 1 week post op to 6 post op]
- Physical assessment by surgeon – IKDC objective
- Patient reported outcomes
 - KOOS, VAS, IKDC subjective, Marx

6 weeks (\pm 5 days)

- Physical assessment by surgeon – IKDC objective
- Patient reported outcomes
 - KOOS, VAS, IKDC subjective, Marx

6 months (\pm 14 days)- To be completed in RedCap

- Patient reported outcomes
 - KOOS, VAS, IKDC subjective, Marx

12 months (\pm 28 days)

- Physical assessment by surgeon – IKDC objective
- Patient reported outcomes
 - KOOS, VAS, IKDC subjective, Marx
- X-rays (merchant view, AP and PA Rosenberg)
- MRI

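### The WPAI endpoint measures change from week 1 to week 6, both after the randomized surgery, so a persisting early arm difference cancels and a shrinking one appears reversed

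*Protocol*

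**What the plan says.** Section 2.2 words the WPAI endpoint as a change, "WPAI V2.0) from 1 week post-op to 6 weeks post-op". The other four change endpoints in that list (VAS, IKDC subjective, IKDC objective, Marx) are taken from baseline, for example "Change in Marx Activity Rating Scale from baseline". The primary endpoint in section 2.1 is also referenced to baseline.

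Section 4.5 puts randomization and the procedure on the day of surgery. Before that, section 4.2 says subjects "will complete all patient reported outcomes (KOOS, VAS, IKDC subjective, Marx"), and the screening list in section 4.5 names the same four instruments. WPAI is in neither. It appears only as a weekly online item: "KOOS activity, VAS, return to work/activity (WPAI V2.0). [To be completed weekly from 1 week post op to 6 post op"].

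Two further statements concern the same weekly data:

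- Section 4.4 states: "Secondary outcomes include time to return to work/activity and time to return to no pain". Section 2.2 lists neither outcome.
- The item "Explanation of the weekly online data to be collected on RedCap" is placed at the visit headed "10 days (7 days-14 days post op").

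**The concern.** A change score in a randomized trial is safe when its starting value precedes treatment, because randomization makes the arms comparable at that point. Here the starting value is taken a week after surgery. If one technique gives less impairment in the first week, that benefit enters the reference value and is subtracted from the result. An arm that is better at both week 1 and week 6 could be reported as no better, or as worse, although the weekly values would show the advantage.

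Two smaller matters are linked to this. The two time-to-event outcomes in section 4.4 have weekly sources (WPAI and VAS) that stop at week 6. After that, VAS and the activity scales (KOOS, IKDC subjective, Marx) are taken only at weeks 24 and 52, and WPAI not at all. And if subjects first hear about the weekly entries at the 10-day visit, the week-1 entry, which is the reference value of the change score, is the one most likely to be late or missed. This last point is an inferred operational risk, not something the protocol states.

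**Working it through.** The protocol gives no figure for this endpoint, so there is nothing to reproduce. The check is algebra followed by an illustration under stated assumptions.

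**Step 1: what the endpoint estimates.** Let d1 and d6 be the advantage of one arm at weeks 1 and 6. The between-arm contrast in change is d6 − d1.

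- Constant advantage, 0.5 SD at both weeks: 0.5 − 0.5 = 0.
- Shrinking from 1.0 to 0.5 SD: 0.5 − 1.0 = −0.5 SD, the wrong sign.
- Equal at week 1, growing to 0.5 SD: 0.5 − 0 = +0.5 SD, undistorted.

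In assumed impairment scores (higher is worse), take radiofrequency 50 and mechanical 60 at week 1. If week 6 is 20 and 30, both arms change by −30 and the contrast is 0. If week 6 is 20 and 22, the changes are −30 and −38, and the contrast of +8 appears to favour mechanical debridement, although radiofrequency is better at both weeks.

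**Step 2: the trend reading.** If the interval is read as a slope over the six weekly values, with even change across five intervals, the slope contrasts per week are 0, −0.5/5 = −0.1 and +0.5/5 = +0.1. The cancellation and reversal remain.

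**Step 3: size.** Section 4.1 plans "enrollment of 82 randomized subjects (to assure 70 subjects complete the study") at 1:1, so n = 70/2 = 35 per arm. Assumed, because the protocol gives no WPAI figures: SD 1 at each week, equal correlation r between weeks of 0.3, 0.5 or 0.7, two-sided 5% test, noncentral t with 68 df.

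- Subject SD of the change = √(2(1 − r)) = 1.183, 1.000, 0.775.
- Subject SD of the six-week average = √((1 + 5r)/6) = 0.645, 0.764, 0.866.
- Subject SD of the week-6 level = 1.
- Standard error of a contrast = SD × √(2/35): change 0.283, 0.239, 0.185; average 0.154, 0.183, 0.207; level 0.239.

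The mean advantage over the six weeks is 0.5, (1.0 + 0.5)/2 = 0.75 and (0 + 0.5)/2 = 0.25 SD in the three cases. Probability of a significant result for r = 0.3 / 0.5 / 0.7:

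| True advantage | Change, week 1 to 6 | Six-week average | Week-6 level |
|---|---|---|---|
| Constant 0.5 SD | 0.05 by chance, half in each direction | 0.891 / 0.770 / 0.663 | 0.541 |
| Shrinking evenly 1.0 to 0.5 SD | 0.414 / 0.541 / 0.759, **wrong direction** | 0.998 / 0.982 / 0.946 | 0.541 |
| Growing evenly 0 to 0.5 SD | 0.414 / 0.541 / 0.759 | 0.358 / 0.271 / 0.221 | 0.541 |

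**Step 4: timing of the explanation.** If week 1 means day 7, the explanation comes 7 − 7 = 0 to 14 − 7 = 7 days after the first entry is due, and 10 − 7 = 3 days after it at the nominal visit.

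**The case against.** - **The contrast is a valid estimate of something.** Under randomization d6 − d1 is the arm difference in recovery between weeks 1 and 6, and the protocol does not say whether it wants improvement or burden. That is fair: the endpoint is coherent if late improvement is the target. But WPAI is collected only in the first six weeks and section 4.4 asks about time to return to work, which points to early recovery, and this endpoint can hide it.
- **The phrase may only describe the collection window.** Section 4.5 uses similar words that way. Section 2.2 nevertheless says change, no other reference value exists, and the trend reading fails in the same way. If levels were intended, the wording still needs correcting. A statistical analysis plan would either inherit the problem or depart from the protocol.
- **The size is hypothetical.** This stands. Nothing in the protocol supports an early difference; the comparative clinical outcomes cited in section 3.1 are at 1 and 4 years, plus time to revision. The calculation uses a two-sided superiority test although the trial is a non-inferiority design, and it counts all completers although work items cannot apply to subjects who are not working. The percentages are illustration only.
- **The alternative does not always win.** This also stands: the six-week average is less sensitive than the change score when the arms are equal at week 1 and separate later.
- **The side points are minor.** A day-7 visit coincides with week 1, KOOS and VAS are collected at that visit in any case, and earlier instruction could be given without being listed. So mainly the first WPAI entry is exposed.

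**Conclusion.** The concern holds. It follows from the text and from arithmetic: both time points are post-treatment, no pre-operative value exists, and the contrast d6 − d1 is zero for a persisting advantage and reversed for a shrinking one. How often this would mislead depends on a week-1 difference that the protocol does not quantify. Under the stated assumptions the wrong-direction rate is 41-76% in the shrinking case, and there is no distortion if the arms are equal at week 1. The endpoint is secondary, and the weekly values needed to avoid the problem are already planned. It should be corrected, but it does not threaten the trial's main conclusion. The mismatch between sections 4.4 and 2.2 is a plain inconsistency; the late explanation of the weekly entries is a lesser, inferred risk.

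**What to change.** 1. In section 2.2, define the endpoint as the between-arm comparison of WPAI levels over weeks 1-6: the six-week average from one repeated-measures model of the weekly values, for all randomized subjects, with the week-6 difference and its confidence interval from the same model. Name the WPAI component used and, if it is a work component, how subjects who are not working are treated.
2. Move the explanation of the weekly online entries to screening or the day of surgery.
3. Reconcile section 4.4 with section 2.2. Either list the two time outcomes in section 2.2, stating which entry counts as return to work/activity and as no pain, how subjects not working before surgery are handled, and censoring at week 6; or delete them from section 4.4.

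**Cost.** The redefined endpoint needs no new data and no extra visit. A pre-operative WPAI is optional for this comparison and would only add precision. If the time outcomes are kept, work status before surgery must be recorded, unless the demographics at screening already capture it. The six-week average loses sensitivity when the arms separate only after week 1 (22-36% against 41-76% in the assumed case), which is why the week-6 difference is reported with it. An explanation at screening is wasted on subjects excluded at arthroscopy. Censoring at week 6 gives up information on later recovery; for pain, treating the time as interval-censored would keep the VAS from weeks 24 and 52.

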2.3 Imaging Endpoints

- ICRS grade of chondral lesion at Week 52 post-op
- MRI assessment at Week 52 post-op

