5.3 Inclusion Criteria

Subjects MUST meet ALL of the following criteria to be included in the study:

- Given written informed consent on the IRB approved consent form specific to the study, prior to study participation
- 18-50 years old
- Male or Female
- Suspected chondral damage in the following locations where debridement is indicated:
 - Medial femoral condyle
 - Lateral femoral condyle
 - Trochlea
 - Patella
- < 30% joint space narrowing as seen on x-ray (merchant view, AP and PA Rosenberg)
- 1 or more chondral lesion(s) as noted on MRI
- Concomitant procedures are allowed unless noted in the exclusion criteria

5.4 Exclusion Criteria:

- Previous chondral treatment in the same compartment (prior debridement and lavage performed more than *three* months prior to baseline are acceptable)
- Focal chondral defect indicated for concomitant procedures (i.e., microfracture, ACI, MACI, OATs)
- Concomitant procedures that are not allowed:
 - Lateral retinacular release
 - Excision of osteophytes
 - Subchondroplasty
 - Manipulation under anesthesia
 - ACL reconstruction
 - Quad tendon repair
 - Patellar tendon repair
 - Patellar tendon debridement
 - Multiligament reconstruction
- Pregnant and/or intending to become pregnant during this study period

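### The ICRS imaging endpoint is fixed as a Week 52 grade only, although the purpose is change in imaging outcomes and the protocol does not state that a starting grade is assigned

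*Protocol*

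**What the plan says.** - **Purpose (Protocol 1.1).** The study is to "evaluate the changes in clinical and imaging outcomes following arthroscopic treatment".
- **Imaging endpoints (2.3).** There are two: "ICRS grade of chondral lesion at Week 52 post-op" and "MRI assessment at Week 52 post-op". Neither refers to baseline.
- **Clinical endpoints (2.1, 2.2).** The primary KOOS endpoint is a change from baseline to Week 52. Four of the six secondary endpoints are changes from baseline, for example "Change in Visual Analogue Scale (VAS) scores from baseline". A fifth is a change from week 1 to week 6, and only satisfaction is a single Week 52 value.
- **Measurement (4.4).** "Baseline MRI will be compared to MRI at 52 weeks to evaluate knee morphology, cartilage signal" and five further features. Lesion grade is not in that list. The next sentence says that an international cartilage repair score will be used, without saying when or on what material.
- **Visits (4.5).** Screening requires an MRI less than 3 months old. The surgery entry lists three arthroscopic checks, randomization and the operation. The 12-month visit lists X-rays and MRI. No visit mentions an ICRS grade.
- **Eligibility (5.3).** Entry requires "1 or more chondral lesion(s) as noted on MRI". No grade criterion is set.
- **Background (3.1).** The cited systematic review found radiofrequency treatment efficient and safe specifically for Outerbridge Grade 2 and 3 lesions, and Grade 4 lesions too advanced to respond well to debridement.

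**The concern.** An endpoint that is a grade at one time point does not measure change. A lesion read as Grade 3 at Week 52 may be an unchanged Grade 3, a worsened Grade 2 or an improved Grade 4, and section 2.3 as written counts all three alike. The stated purpose is to tell them apart.

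Starting grade matters here because the protocol's own background ties response to it. Section 5.3 does not restrict it, and no section says that it will be assigned. At stake is whether the ICRS result can speak to progression or healing, whether readers can see that the arms began alike, and how precise the comparison is.

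**Working it through.** The plan gives no figure for this endpoint, so there is nothing to reproduce. The check sets the sections side by side and then sizes the precision at stake under a stated assumption.

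**1. Purpose against endpoint.** Section 1.1 asks for change and 4.4 describes a baseline-to-52-week MRI comparison. Section 2.3 gives Week 52 only for both imaging endpoints. It therefore departs from 1.1, from 4.4 and from the change wording of most endpoints in 2.1 and 2.2.

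**2. Is a starting grade stated anywhere?** Sections 4.2 and 4.5 secure a baseline MRI, 4.5 includes an arthroscopic check before randomization, and 5.3 requires a lesion on MRI. None says that an ICRS grade is assigned. The score sentence in 4.4 could cover both scans or only the later one. The source material exists for every subject, but the instruction to grade it does not appear.

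**3. Which modality?** The 12-month visit in 4.5 lists no second arthroscopy, so the Week 52 grade has to come from imaging, in practice the MRI. The like-for-like starting value is a grade read on the screening MRI. An arthroscopic grade is useful as a descriptor, but subtracting it from an MRI grade would mix measurement methods.

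**4. Which lesion?** Section 2.3 speaks of one lesion. Section 5.3 admits one or more, and 3.1 describes subjects with multiple lesions. Change per subject is undefined until the lesion or lesions are named.

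**5. What the Week 52 comparison still delivers.** Section 4.1 randomizes 1:1, so the difference between arms in Week 52 grade is a valid estimate without a baseline grade. Three things are lost: within-subject change, the balance check and precision.

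**6. Size of the precision loss (assumption).** Let r be the correlation between starting and Week 52 grade. The documents do not give it; take 0.4 to 0.7. Treat grade as approximately numeric, with equal variance at both times. Variances below are relative to the unadjusted Week 52 grade.

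- Adjusted for starting grade: 1 − r². At r = 0.4 this is 1 − 0.16 = 0.84; at r = 0.7 it is 1 − 0.49 = 0.51. Adjustment removes 16% to 49% of the variance. The standard error is multiplied by √0.84 = 0.92 to √0.51 = 0.71.
- Simple change in grade: 2(1 − r). At r = 0.4 this is 1.20; at r = 0.7 it is 0.60.

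Simple change serves the descriptive purpose in 1.1, but it can be noisier than the Week 52 value when r is below 0.5. The adjusted comparison is more precise at both ends of the range.

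**The case against.** **The starting grade may well be collected.** In 4.4 the cartilage score follows directly on the baseline-to-52-week comparison, and the natural reading is that it applies to both scans. Section 4.5 lists procedures, not the items read from them, and it lists no MRI reading items at 12 months either. This stands. A reader might infer that no starting grade is recorded, or that the starting state of a lesion cannot be recovered. The documents support neither, because every subject has a screening MRI and an arthroscopy and a grade could be read from the stored scan. The gap is that the protocol does not say it will be done.

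**Randomization protects the comparison.** This also stands. A reader might infer that a chance difference in starting grade would bias the Week 52 result. It would not: such differences are ordinary sampling variation, already reflected in the standard error of the comparison. Nor do the documents show that the trial is unstratified or that starting grades vary widely. The randomization method is not described. Sections 5.3 and 5.4 narrow the population through the indication for debridement, the joint-space limit and the exclusion of focal defects indicated for other cartilage procedures.

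**Adjustment and categories belong in the SAP.** This stands in part. The model and the grouping of outcomes can be left to it. What the endpoint is, and which values are collected to form it, belong in the protocol, and there sections 1.1, 2.3 and 4.4 do not agree.

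**It is only an imaging endpoint.** True, and it limits the weight of the point.

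**Conclusion.** The point holds as a mismatch between the stated purpose and the endpoint definition. Section 2.3 fixes the ICRS outcome at Week 52, 1.1 and 4.4 look for change, and no section states that a starting ICRS grade is assigned. The Week 52 comparison is valid but does not answer the question about change. It also gives up a balance check on a characteristic that the background treats as prognostic. The background uses Outerbridge grades, so carrying this over to ICRS grade is a reasonable inference, not a statement of the protocol.

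The precision forgone is 16% to 49% of variance only under the assumed correlations of 0.4 to 0.7; the documents supply no value. The primary KOOS analysis is unaffected. The point merits correction mainly because the remedy is so cheap.

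**What to change.** Reconcile sections 1.1, 2.3, 4.4 and 4.5:

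- **4.5, screening:** assign an ICRS grade to each chondral lesion on the screening MRI, using the scale and modality to be used at Week 52, so that a grade exists for every lesion later treated.
- **4.5, surgery:** record which lesions were treated and their arthroscopic grade, as a descriptor and not as the baseline for change.
- **4.4:** state that the cartilage score is applied to both the baseline and the 52-week MRI, and whether it is the same measure as the ICRS grade in 2.3.
- **2.3:** define the endpoint as change in ICRS grade of the treated lesion(s) from screening MRI to Week 52 MRI, or as Week 52 grade compared between arms with adjustment for starting grade. Fix in advance how several lesions in one subject are summarised; the worst treated lesion is one option. Give the second imaging endpoint the same baseline reference.

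The model and any grouping into worsened, unchanged and improved can be left to the SAP. The scans and the arthroscopy already take place, so no procedure or reader is added. The cost is a few data fields and a little more reading time per scan. If enrolment has begun, stored screening MRIs can be graded retrospectively, ideally by a reader unaware of allocation.
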